## **LIST OF ABBREVIATIONS**

AE	Adverse Event/Adverse Experience
DM	Diabetes mellitus
HIPAA	Health Insurance Portability and Accountability Act
PTT	Penile traction therapy
PD	Peyronie's Disease
RCT	Randomized controlled trial

## Study Summary

Title	Penile Length Restoration in Men with Diabetes Mellitus, Type II
IRB Protocol Number	18-006696
Methodology	Controlled randomized study
Overall Study Duration	3 years
Subject Participation Duration	6 months
Objectives	Evaluate the efficacy of the RestoreX penile traction device in restoring length loss secondary to diabetes mellitus
Number of Subjects	120
Diagnosis and Main Inclusion Criteria	Men with diabetes mellitus, type II
Study Device	RestoreX®, penile traction therapy
Duration of Exposure	Subjects in Groups 1-3 will use device for 3 months for 30 minutes, twice daily. Subjects in Group 4 will be control and will not use the device.  After the randomized period, subjects using the device will switch to not using the device (Group 1), using the device once weekly x 30 minutes (Group 2), or continuing to use the device twice daily x 3 months (Group 3).
Reference therapy	The use of the device will be compared against a control group using no traction therapy. Individuals will also be compared to themselves to evaluate changes from baseline.
Statistical Methodology	Stratification of subjects prior to randomization to assure an equal representation based on baseline penile length. Statistical comparisons will be made comparing total penile length prior to and following therapy. Comparisons of subjective questionnaire responses will also be made between groups and at the various time points captured.

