### 2.2 Secondary Objectives

1. Compare patient compliance with traction device.
2. Compare patient reported satisfaction with use of traction device.
3. Evaluate any adverse events (AEs) with use of RestoreX® for penile lengthening.
4. Compare the rate of Peyronie's disease development among groups
5. Compare patient satisfaction scores including satisfaction with overall penile length.
6. Evaluate and compare patient erectile function among groups
7. Review associations between DM factors and standardized questionnaires and outcomes

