### 3.4 Consent and Enrollment

Patients wishing to enroll in the study will be given the opportunity to meet with the study coordinator to further review study details and formal consent.

Patients that would like additional time to consider their participation will be given other opportunities to meet with the study coordinator if desired. If the patient expresses interest in participating at any of these times, a formal consent will be reviewed (see **Attachment – Consent Form**).

At enrollment, all participants will be assigned a study identifier, with a master list maintained in a password protected database (Mayo server – RAVE database) linking the patient to the identifier. A total of 30 patients will be enrolled into each arm of the study for a total of 120 patients enrolled overall. It is estimated that up to 360 patients will need to be screened to enroll the 120 patients.

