### 3.5 Study Schema

All patients will have been previously seen at Mayo Clinic for a condition of DM. Following enrollment, key factors relating to their underlying condition will be abstracted from the chart by a study coordinator, including age, duration of disease (if known), number of DM medications, use of insulin, most recent fasting glucose and HbA1c, creatinine, and testosterone, HOMA1-IR, HOMA2-IR, and BMI. If any of these variables are not available, no additional attempts will be made to retrieve the information.

At the initial appointment, patients will also undergo a penile length assessment by a urology provider and Men's Health Nurse and receive questionnaires (IIEF-15 and disease specific history)

Once consent and study assessments are completed, the patients will be randomized into one of four groups:

1. PTT for 30 min 2x/day x 3 months, followed by no treatment x 3 months
2. PTT for 30 min 2x/day x 3 months, followed by once weekly (30 minutes) x 3 months
3. PTT for 30 min 2x/day x 6 months
4. Control (no treatment)

Patients in the treatment arm will record a daily journal of their usage of the device. Patients will then begin using the device as instructed for the times appropriate to their group.

After 3 months of using the device (+1.5 months permitted), patients will return for subsequent assessments (see below) and a follow-up questionnaire. At this time, patients will be encouraged to report any adverse events. They will also be requested to bring their device back to the clinic to review proper usage and any questions on the device. After completion of the subsequent assessments, patients will begin the second phase of the trial.

After 6 months (+ 1.5 months permitted) patients will return to the clinic to undergo final assessments, which are identical to the 3-month assessments.

Since participants are being asked to travel to Mayo Clinic for subsequent assessments, we will provide a remuneration amount of up to \$600. The purpose is to assist participants in their travel to and from Mayo Clinic. Those that provide consent will be provided \$100 after their baseline assessment. After their second and third visits (3 and 6-months, respectively), they will receive \$250 for a possible total of \$600.

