#### 5.2 Statistical Analysis

Analyses will be performed using comparisons within patients of same baseline penile stretch length and between groupings of varying lengths. Comparison of penile length between traction and no traction will be made, as well as reviewing historical records to increase statistical power. Comparison of length from baseline to post-traction for individual participants will also be reviewed.

The data will also be analyzed in three ways: 1- with all patients included, regardless of their compliance to utilize the device for the recommended treatment time, 2- with patients excluded if they failed to achieve 90% compliance with the recommended duration of treatment, 3- with patients excluded if they failed to achieve 75% compliance with the recommended duration of treatment. Factors which will also be included to determine compliance will include frequency and duration of use and whether or not the device was used correctly (black rods buried, amount of time white line showing).

Comparisons will also be made on other subjective and objective variables obtained including number of adverse events, complications, subjective responses to questionnaires, or other information. All data will be normalized by baseline stretched penile length.

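### Baseline IIEF-15 is collected but has no stated role in the between-group comparison of erectile function; adjusting for it would add precision at no cost

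*Combined protocol and SAP*

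**What the plan says.** Section 2.2 includes the objective "Evaluate and compare patient erectile function among groups". The IIEF-15 is given at baseline, month 3 and month 6 (sections 3.5, 4.1 to 4.3 and 4.5).

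Two places describe how questionnaire data will be analysed:

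- Study Summary, Statistical Methodology: "Comparisons of subjective questionnaire responses will also be made between groups and at the various time points captured".
- Section 5.2: "Comparisons will also be made on other subjective and objective variables obtained including number of adverse events, complications, subjective responses to questionnaires, or other information".

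Neither names a model, a covariate or a change score for the IIEF-15. Two further sentences concern baseline values. The Study Summary, under reference therapy, says "Individuals will also be compared to themselves to evaluate changes from baseline", without naming an outcome. Section 5.2 says "All data will be normalized by baseline stretched penile length". Stretched penile length is also the only stratification factor (section 3.6).

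On size, section 3.4 says "A total of 30 patients will be enrolled into each arm of the study for a total of 120 patients enrolled overall".

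**The concern.** A man's erectile function at follow-up is likely to depend on where he started. The design does not balance starting erectile function: stratification uses length alone, and the entry criteria in section 3.1 set no limit on erectile function score. The stated analysis does not bring the starting score in either. Normalizing by penile length adjusts for a different characteristic, and it is unclear what scaling a questionnaire score by a length would mean.

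What is at stake is precision. With arms of 30, the groups can differ at baseline by chance to an extent that matters, and part of that difference reappears at months 3 and 6. Section 1.4.2 says it is not known whether traction helps or harms rigidity, so even the sign of the estimate is of interest. The covariate that would sharpen the estimate is already on the case report forms. If its use is not fixed in advance, the choice will be made after the data are seen.

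**Working it through.** **Inputs from the documents.** Four arms of 30, and 4 × 30 = 120, which agrees with section 3.4. The plan gives no alpha, power, effect size, IIEF-15 SD or correlation, so there is no power figure to reproduce.

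**Assumptions.** Equal SD at baseline and follow-up; baseline to follow-up correlation rho from 0.3 to 0.8; no dropout; two-sided alpha of 0.05; 80% power for detectable differences; an effect of 0.5 SD for the power figures. Normal approximations are used, ignoring the few degrees of freedom that the covariates take up.

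**Step 1: chance baseline gap.** SE = sqrt(1/n1 + 1/n2), in SD units.

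- 30 v 30: sqrt(1/30 + 1/30) = 0.258. The 95% range is ±1.96 × 0.258 = ±0.51 SD. A gap of at least 0.25 SD in either direction has probability 33%.
- 90 v 30: sqrt(1/90 + 1/30) = 0.211, with a 95% range of ±0.41 SD and a probability of 24%. This pools Groups 1 to 3 against Group 4. It applies at month 3 only, because the three regimens are the same until then and differ afterwards (section 3.5).

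**Step 2: how much carries forward.** An unadjusted follow-up difference carries rho times the baseline gap. For a one-SE gap with 30 v 30, this is rho × 0.258.

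**Step 3: variance relative to raw follow-up scores.** ANCOVA: 1 − rho². Change score: 2(1 − rho). The equivalent unadjusted arm size is 30/(1 − rho²).

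| Assumed rho | Shift from a one-SE gap (SD) | ANCOVA variance factor | Variance saved | Equivalent n per arm | Change-score variance factor |
|---|---|---|---|---|---|
| 0.3 | 0.08 | 0.91 | 9% | 33 | 1.40 |
| 0.5 | 0.13 | 0.75 | 25% | 40 | 1.00 |
| 0.7 | 0.18 | 0.51 | 49% | 59 | 0.60 |
| 0.8 | 0.21 | 0.36 | 64% | 83 | 0.40 |

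**Step 4: what this means for 30 v 30.** The detectable difference is (1.96 + 0.84) × SE × sqrt(variance factor). With raw scores it is 0.72 SD. With ANCOVA it is 0.69, 0.63, 0.52 and 0.43 SD at rho 0.3, 0.5, 0.7 and 0.8. Power for a 0.5 SD effect rises from 49% to 53%, 61%, 77% and 90%. For the pooled 90 v 30 comparison at month 3, it rises from 66% to 70%, 78%, 91% and 98%.

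**Step 5: the change score.** Since 1 − rho² = (1 − rho)(1 + rho), and 1 + rho is below 2 for any rho below 1, ANCOVA has the smaller variance throughout. A change score only matches raw follow-up scores at rho 0.5 and is worse than them below that.

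**The case against.** The strongest reply is that the plan is silent here and has not chosen a wrong analysis. A reader might infer from the Study Summary that follow-up scores will be compared visit by visit with baseline deliberately left out. The documents do not say that. The sentence on questionnaires can be read as two comparisons, one between groups and one across visits, and baseline is itself one of the visits. The sentence on comparing individuals with themselves follows directly on the comparison with control and does not rule out comparing changes between groups. This objection stands: the defect is an unstated role for baseline. It does not remove the point, because the self-comparison sentence is not tied to the IIEF-15 or to a contrast with Group 4, and a change score would be the weaker choice anyway.

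A reader might also infer that the result would be biased, or that a follow-up difference could be nothing but the starting difference. Neither follows. Randomization makes the unadjusted comparison unbiased on average, and its standard error already includes chance imbalance. Only rho times a gap carries forward: at rho 0.5 to 0.8, a 0.25 SD gap shifts the result by 0.25 × 0.5 = 0.13 to 0.25 × 0.8 = 0.20 SD. Imbalance and lost precision are largely one harm seen from two sides.

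The size of the gain rests on a correlation that the documents do not give, and at rho 0.3 it is modest. Nor do they give the baseline score distribution; the lack of an entry limit does not show that men will span the whole scale. Finally, this is one of seven secondary objectives, and section 5.2 names no model for any outcome. These points limit the priority of the change, but they are no reason to leave a collected baseline score without a role.

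**Conclusion.** The point holds as a free improvement on a secondary objective. The plan calls for a between-group comparison of erectile function and collects the baseline score, but gives that score no role in the contrast. The only baseline adjustment it states for all data, by penile length, does not replace it. The plan does not say that baseline IIEF-15 will be excluded, and nothing here shows bias.

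The loss is in precision. Adjustment would save 9% of the variance at an assumed rho of 0.3, 25% at 0.5 and 64% at 0.8, equivalent to about 33, 40 and 83 men per arm instead of 30. The standard errors of a chance gap, 0.26 SD for 30 v 30 and 0.21 SD for the pooled month-3 comparison, follow from the planned arm sizes alone. The variance and power figures depend on the assumed rho, equal SDs and no dropout.

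**What to change.** In section 5.2 and the Study Summary:

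- Specify the between-group IIEF-15 analysis as an ANCOVA of the follow-up score on group, or a mixed model covering months 3 and 6, with baseline IIEF-15 score and length stratum as covariates. Name the score to be analysed (erectile function domain or total).
- Report adjusted differences from Group 4, with confidence intervals, at each of months 3 and 6. If Groups 1 to 3 are pooled, limit this to month 3.
- State that normalization by penile length does not apply to questionnaire scores.
- Keep raw scores by visit, if wanted, as descriptive summaries.

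The cost is wording in the plan, settled before the outcome data are examined. The baseline score is already collected, so no extra visits, measurements or patients are needed.

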## 1 Introduction

This document is a protocol for a human research device study. This study will be carried out in accordance with the procedures described in this protocol, applicable United States government regulations and Mayo Clinic policies and procedures.

### 1.1 Background

Men with diabetes mellitus experience sexual dysfunctions at an earlier age and higher rate compared to men without diabetes. One of these sexual dysfunctions includes diminished penile length. It is currently unknown if the decreased length is due to earlier erectile dysfunction or secondary to diabetes itself. Penile traction therapy is one of several treatments which have been used historically to treat decreased penile length, however, to date, no studies have evaluated the role of traction therapy in men with diabetes. The objective of the current study is to evaluate the efficacy of the RestoreX penile traction device (developed by Mayo Clinic and licensed to PathRight Medical) in restoring penile length in men with established diabetes mellitus.

### 1.2 Investigational Device

RestoreX is a PTT device developed by PathRight Medical using technology licensed from the Mayo Clinic. The device is classified as class I (orthotic) and does not require clinical trials to prove safety or efficacy. Mayo Clinic is currently conducting a randomized clinical trial to evaluate several clinically relevant factors including safety, comfort, and preference and to provide preliminary data on dosing and efficacy (IRB 17-001283).

The device has two functional aspects. The first is the ability to provide direct traction on the penis. The second is the ability to provide counter-bending forces, to treat conditions such as Peyronie's disease (bent penis). In the current study, only the direct traction aspects of the device will be investigated.

### 1.3 Preliminary Data

Currently, there is a small amount of preliminary data available on the RestoreX® instrument. During the developmental phase of the device, a quality improvement project was performed to evaluate the clamping portion. It was determined that the clamp represented the most critical aspect of the device, as this was where the majority of discomfort occurred with other devices. Additionally, the clamp needed to provide sufficient friction to allow adequate traction without having the glans of the penis dislodge from the device.

A total of 15 patients participated in the quality improvement project and had the clamps applied under direct supervision for 30 minutes. After the 30 minutes, all patients reported 0/10 pain, and only minimal transient erythema was documented by the physician. The clamp was again applied, and traction forces were administered to determine if the clamp was able to remain intact despite stretching forces applied. This also resulted in a successful

outcome, with all patients able to successfully achieve a minimum required tension of 1 kg, with a 36% safety factor achieved before any discomfort was reported among any patient. During the testing, patients reported improved comfort with the use of a wrap such as gauze or Coban, which permitted additional traction in all patients.

Regarding background data on the RestoreX device, currently, Mayo Clinic is conducting a randomized clinical trial evaluating its role in men with PD (IRB 17-001283). Preliminary data have demonstrated efficacy of the device with all end points (improvement in length, curvature, satisfaction, and standardized questionnaires). Detailed information is also captured on adverse events. Among men in the treatment group, the most common adverse events were erythema (31%), cold glans (4%), and minor discomfort (52%). All symptoms resolved within 5 minutes of discontinuing use, with the exception of one patient (4%) who experienced minor discomfort for 15 minutes. Findings are consistent with other traction device studies.

## **1.4 Study Rationale and Risk Analysis (Risks to Benefits Ratio)**

### **1.4.1 Study Rationale**

PTT has been shown to improve penile length in several clinical scenarios, including following penile surgery, as a primary lengthening therapy, and in men with conditions which shorten the penis such as PD. To date, no studies have evaluated the role of PTT in restoring penile length in men with diabetes mellitus (DM), a condition known to result in decreased penile length. The current study is designed to address this gap in the literature.

### **1.4.2 Potential Benefits**

There are several potential benefits to using PTT. As loss of penile length results in several issues including loss of sexual function, cosmetic concerns, and difficulty in maintaining hygiene (incontinence resulting in yeast infections), the ability to maintain or restore length may mitigate these issues. Additionally, men with DM have an increased rate of development of penile curvature (PD), which can be both functionally and psychologically distressing. PTT has previously been demonstrated to limit the extent of penile curvature that men experience among those with early PD, and therefore, the use of PTT in men with DM may reduce the likelihood of either developing the condition or in lessening the extent of the condition. It is unclear if PTT will impact (improve or worsen) erectile rigidity in men with DM, although preliminary data from the current PTT study in men with PD (IRB 17-001283) has demonstrated improvements in erectile function.

## **1.5 Anticipated Duration of the Clinical Investigation**

The overall study will be scheduled for 3 years, to permit adequate time for enrollment and follow-up. The intervention phase will include 6 months of randomized treatment (for the treatment arm).

## 2 Study Objectives

### 2.1 Primary Objective

1. The primary objective is to assess penile length pre and post completion of RestoreX® traction therapy compared to control groups (no treatment) of DM subjects.

### 2.2 Secondary Objectives

1. Compare patient compliance with traction device.
2. Compare patient reported satisfaction with use of traction device.
3. Evaluate any adverse events (AEs) with use of RestoreX® for penile lengthening.
4. Compare the rate of Peyronie's disease development among groups
5. Compare patient satisfaction scores including satisfaction with overall penile length.
6. Evaluate and compare patient erectile function among groups
7. Review associations between DM factors and standardized questionnaires and outcomes

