## 4 Study Procedures

### 4.1 Baseline Assessments

- Participant consented
- Abstracted from chart
  - Age
  - Duration of DM
  - DM medications including use of insulin
  - Fasting glucose, HbA1c, HOMA1-IR, HOMA2-IR, creatinine, testosterone
  - BMI
- Objective assessments
  - Penile length – pubic symphysis to glanular corona
- Subjective questionnaires
  - Disease specific history
  - IIEF-15
- Device usage diary provided for treatment group

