#### 4.4 Assessment of Length

Penile length measurements will be obtained by a member of the clinical team using a measurement from the pubic symphysis to the corona of the glans penis. Measurements will be obtained at baseline and at the 3 and 6 month follow-ups.

See **Attachments – Device Usage Diary, Disease Specific History, IIEF-15, Questionnaire 3 Month and 6 Month**

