#### 4.5 Schedule of Events

**Table 1: Schedule of Events**

Study Activity	Baseline Assessment	3 Month	6 Month
Consent	X		
IIEF-15	X	X	X
Disease Specific History	X		
Length Assessment	X	X	X
Patient Diary Provided	X	X	
Questionnaire 3 Month		X	
Questionnaire 6 Month			X

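### No baseline satisfaction-with-length item is identified for Objective 5; unless the baseline forms already hold one, adding it before randomization would allow within-man change and a more precise comparison

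*Combined protocol and SAP*

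**What the plan says.** - **Objective.** Section 2.2, Objective 5: "Compare patient satisfaction scores including satisfaction with overall penile length". It names no instrument or time point, and does not say whether the score is a level or a change.
- **Planned comparisons.** The Study Summary states: "Comparisons of subjective questionnaire responses will also be made between groups and at the various time points captured". It also says, in general terms, that men will serve as their own comparison for change since baseline.
- **Baseline forms.** Section 4.1 lists the disease-specific history and the IIEF-15 under "Subjective questionnaires". Section 3.5 agrees, and places randomization after these assessments.
- **Schedule.** In Table 1 (section 4.5), the IIEF-15 is marked at all three visits and "Disease Specific History" at baseline only. "Questionnaire 3 Month" is marked at month 3 only, and "Questionnaire 6 Month" at month 6 only.
- **Contents of the forms.** Section 4.4 refers the reader to "Attachments – Device Usage Diary, Disease Specific History, IIEF-15, Questionnaire 3 Month and 6 Month". These are not reproduced, so their items cannot be read.
- **Analysis.** Section 5.2 compares questionnaire responses and normalizes all data by baseline stretched length. It mentions no adjustment for a baseline questionnaire score.

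**The concern.** Satisfaction with length is an outcome on which men differ before any treatment. Entry under section 3.1.1 requires only type 2 diabetes and age 18 or over, so men are not selected for length loss or for dissatisfaction with it. The forms written for the follow-up visits first appear after three months of treatment, and the text points to no earlier score on the same item.

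Two things depend on such a score. One is the comparison of each man with his own baseline, which the Study Summary announces. The other is precision: with 30 men per arm, a good share of the variation in follow-up satisfaction may simply reflect where each man started, and a baseline covariate would remove that share. A baseline score cannot be recovered once treatment has begun.

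**Working it through.** **1. Count of administrations in Table 1**

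| Form | Baseline | Month 3 | Month 6 |
|---|---|---|---|
| IIEF-15 | yes | yes | yes |
| Disease-specific history | yes | no | no |
| 3-month questionnaire | no | yes | no |
| 6-month questionnaire | no | no | yes |

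Baseline is therefore not free of questionnaires. A pre-treatment satisfaction-with-length score exists only if the history or the IIEF-15 contains one. Because the history is given once, an item in it is useful for change only if the follow-up questionnaires repeat it on the same scale.

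**2. Inputs for the size of the loss**

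- From section 3.4: 30 men per arm in four arms, 4 × 30 = 120. The plan gives no power basis for this total and no figure for satisfaction, so there is no planned precision to reproduce.
- Assumed: a correlation r of 0.4, 0.6 or 0.7 between baseline and follow-up satisfaction; a linear relation with equal variances; no dropout. For detectable differences: two-sided 5% level and 80% power (1.96 + 0.84 = 2.80).

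**3. Effect of adjusting for baseline**

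Residual variance is multiplied by 1 − r², and the standard error by √(1 − r²). The one degree of freedom spent on the covariate is ignored.

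| r | 1 − r² | √(1 − r²) | Reduction in standard error |
|---|---|---|---|
| 0.4 | 0.84 | 0.917 | 8% |
| 0.6 | 0.64 | 0.800 | 20% |
| 0.7 | 0.51 | 0.714 | 29% |

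**4. The same in detectable differences (SD units)**

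- One device arm against control, no covariate: 2.80 × √(1/30 + 1/30) = 2.80 × 0.258 = 0.72. With the covariate: 0.72 × 0.917 = 0.66, 0.72 × 0.800 = 0.58, 0.72 × 0.714 = 0.52.
- Month 3, when Groups 1 to 3 have had the same regimen and could be pooled: 2.80 × √(1/90 + 1/30) = 2.80 × 0.211 = 0.59. With the covariate at r = 0.7: 0.59 × 0.714 = 0.42.

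**5. Why adjustment and not a simple change score**

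A change score has variance 2(1 − r) relative to the follow-up score: 1.2 at r = 0.4, 0.8 at r = 0.6 and 0.6 at r = 0.7. At r = 0.4 it is noisier than using no baseline at all (1.2 against 1.0). The adjusted analysis has the lower variance at each of these values (0.84, 0.64, 0.51).

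**The case against.** Much of the case against this point is sound.

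- **Unseen forms.** A reader might infer from Table 1 that change in satisfaction cannot be measured. The documents do not support that. Two questionnaires are given at baseline, either could carry a satisfaction item, and what sits in an attachment that is not reproduced cannot be counted as missing. What can be said is that the text identifies no such item.
- **Validity.** A reader might also infer that follow-up scores cannot be interpreted without a starting value. That overlooks the concurrent randomized control. Objective 5 asks only for a comparison, and comparing follow-up levels between randomized arms is unbiased without any baseline.
- **Chance imbalance.** One could add that, with 30 per arm, a baseline difference of √(2/30) = 0.26 SD or more arises about 1 time in 3. That is true of any unmeasured covariate in a trial of this size. It is already contained in the standard error of the follow-up comparison and is not a second harm on top of the lost precision.
- **Length as a proxy.** Stratifying by stretched length (section 3.6) and normalizing by it (section 5.2) might capture some of the variation in satisfaction if the two are related. The documents give no information on how closely, and neither step adjusts for a man's own earlier score.
- **Importance.** This is one of seven secondary objectives, and the primary outcome does have a baseline measurement.

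What remains is that no matching baseline item is named, no adjustment for one is planned, and the Study Summary nevertheless announces comparison with baseline.

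**Conclusion.** The point stands as an inexpensive improvement, not as a flaw that invalidates Objective 5. The text names no baseline satisfaction-with-length score and plans no adjustment for one. If the baseline forms do hold the same item, all that is lacking is a statement of it and its use in the analysis. If they do not, within-man change on this outcome cannot be estimated, and the between-group comparison, although unbiased, has a standard error that adjustment would reduce by about 8% to 29%. That range rests wholly on the assumed correlations of 0.4 to 0.7; the documents give none.

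There are two limits. Satisfaction with use of the device (Objective 2) has no meaningful pre-treatment value and is not affected. A baseline score also does not remove reporting bias at follow-up: section 3.6 has the assignment explained to each man, so men will answer the later questionnaires knowing their arm.

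**What to change.** 1. Check whether the disease-specific history or the IIEF-15 contains the same satisfaction item that the follow-up visits use. If so, name the item and its form in section 4.1 and identify it in section 5.2 as the baseline for Objective 5.
2. If not, add the satisfaction items of the 3-month and 6-month questionnaires that do not concern the device to section 4.1 and to the baseline column of Table 1. They should be completed before randomization, with identical wording and response scale at all three visits.
3. In section 5.2, state that groups are compared on the follow-up satisfaction score adjusted for the baseline score, and say which visit is compared.
4. If a baseline item is not added, state that Objective 5 compares follow-up levels only, and that the Study Summary's comparison with baseline does not extend to this outcome.

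The cost is a few more items on paperwork already completed at the first visit, a few minutes per man. It needs no extra visit or staff and no more men.
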